11 STATISTICAL METHODS

11.1 Sample Size Estimation

Sample size calculations were performed using nQuery 8 software. Sample sizes per group will vary between 100 (for the AstraZeneca and Sputnik-primed groups) and 200 (for the Sinopharm-primed groups). The Sinopharm vaccinee impact is of greater importance to Mongolia as this is the main vaccine used for the primary series in Mongolia. In addition, Sinopharm is the least effective of the 3 vaccines used, so we expect to see evidence of more breakthrough cases and therefore a wider range of pre-booster immunity levels. Precision-based sample size calculations were performed based on the reactogenicity outcomes. Assuming the percentage of participants reporting local or systemic reactions is 50%, a sample size of 200 participants will produce a 95% confidence interval that extends 6.9 percentage points from the observed percentage. With a sample size of 100, the 95% confidence interval will extend 9.8 percentage points from the observed percentage. For immunogenicity, sample size calculations were based on the comparison of seroresponse rates between the standard and fractional dose groups within the non-inferiority framework. Assuming a -10% non-inferiority margin and a seroresponse rate of 95% in both arms, the study will have >99% power for the non-inferiority comparison using 200 participants per group. Under the same assumptions, the study will have 90% power with 100 participants per group for the non-inferiority comparisons.

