11.3 Methods of analysis

Reactogenicity following immunisations will be presented as the number and percentage of participants self-reporting local reactions (pain, tenderness, redness, hardness, swelling, warmth, itch at or near the injection site) and systemic reactions (fever, nausea, vomiting, diarrhoea, headache, fatigue/malaise, myalgia), and the severity of these reactions (mild, moderate, severe, life-threatening or fatal). Reactogenicity data will be presented separately by group and time point.

For immunogenicity, antibody levels will be presented as geometric mean titres (GMT) with 95% confidence intervals. Changes from baseline will be expressed as geometric mean fold ratios (GMFR), calculated as the ratio of the post-booster GMT to the baseline GMT. Seroresponse will be defined as a 4-fold rise in post-booster antibody levels compared to baseline (or >2-fold rise if the baseline (prebooster) antibody level was >=200 BAU/ml). To assess the non-inferiority of the fractional dose compared with the standard dose, comparisons will be based on the difference in percentage of participants with seroresponse. Using a non-inferiority margin of -10% (fractional-dose minus standard dose), non-inferiority will be declared if the lower limit of the 95% confidence interval around the difference in percentages is greater than -10%, where confidence intervals are calculated using Scorebased methods (12).

Analyses will be performed using Stata software (13). Detailed methodology will be outlined in a separate Statistical Analysis Plan.

We will also do a sub-analysis to explore the difference between participants who have/haven't had previous natural infection.

Primary outcome (All samples at all timepoints)

The binding IgG data using the Euroimmun S1 IgG ELISA kits will be reported as relative units/ml (RU/ml) as per manufacturer's instructions. A result of <8 RU/ml: negative (IgG Antibodies for SARS-CoV-2 are not detected), \geq 8 to <11 RU/ml: borderline (IgG antibodies is indeterminate/equivocal with this sample, \geq 11 RU/ml: positive (IgG antibodies for SARS-CoV-2 are detected). Conversion to binding antibody units (BAU/ml) will also be done using the WHO reference serum from NIBSC, UK. Data will be presented as geometric mean titres and 95% confidence intervals.

Analysis comparing fractional and standard dose groups will be based on seroresponse rate (SRR) at 28 days post study vaccine, defined as:

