3.5 BLINDING

Study staff involved in administering the vaccine will be unblinded. The participants and study staff involved in assessing reactogenicity will be blinded to their group allocation until the Day-28 visit. Study staff involved in assessing immunogenicity outcomes will remain blinded during the analysis of specimens. In the unlikely event that it becomes necessary to unblind prior to the Day-28 visit that decision will be taken by the PI, and the participant and physicians who may be caring for the participant will be made aware of the allocation. Statisticians and analysts will remain blinded during the development of the SAP (approved by the Trial Steering Committee). Further, statisticians and analysts will develop and finalise all codes using a dummy variable for treatment allocation. If SAP revisions related to comparative analyses are required after codes have been run using the real allocations, the staff involved in deciding, writing, and approving these revisions will not have access to the data with the real allocations.

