6 STATISTICAL METHODOLOGY

6.1 GENERAL METHODOLOGY

6.1.1 Summary of changes compared to the protocols

- "Functional antibodies" have been described more precisely as "ACE2 binding inhibition by neutralising antibody" in the SAP.
- The SAP added to the definition of seroresponse a specification for participants with binding antibody levels under the limit of detection.
- The "interim analysis" described in the protocol is considered in the SAP as the final
 analysis of the Day-28 endpoints as the intention is to only conduct this analysis
 once all Day-28 data is available (no interim analyses are specified in the SAP).
- Grading for hardness and swelling in Mongolia will not consider interference with daily activities as per the protocol as this information is not being captured.
- The protocol does not specify blinding/unblinding of statisticians and data analysts (only specified for participants, those evaluating reactogenicity, vaccinator, immunologists and laboratory staff, clinical investigators); details on blinding of statisticians and data analysts are specified in this SAP.
- In the Mongolia trial protocol, warmth and itch are binary presence/absence variables, with presence falling under Grade 3 and 4 reactions; in the SAP, warmth and itch are to be analysed as binary presence/absence variables with no grading.
- The BCOV22 protocol specifies non-inferiority analyses in terms of seroresponse at Day-28 (from BCOV21), Month-6, and Month-12. The analysis of Day-28 binding antibody data from BCOV21 has already been conducted by the BCOV21 investigators, and this SAP does not specify re-analysis of this data. Further, Month-6 and Month-12 analyses specified in this SAP are based on the superiority framework and will use continuous data only (a binary seroresponse variable will not be considered).

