6.1.4 Validation of results

Details of data cleaning and verification, including consistency and range checks, are specified in the Data Management Plan. The analysis of the primary immunological endpoint, including any derivation of outcomes and/or covariates from raw data, will be independently double programmed by two analysts prior to unblinding using a randomly generated dummy variable for treatment allocation; discrepancies in results will be resolved by consensus.

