6.13 ANALYSIS OF THE PRIMARY ENDPOINTS

Table 10. Estimand-to-Analysis table⁵ for seroresponse at Day-28 (primary immunogenicity endpoint)

Primary Objective (as pe	er Protocol): Assess and compare the	e immune response measured as binding antibodies (IgG)	
following standard versu	s fractional doses of either trial vacc	ine given as a single additional dose to adults 18 years or	
older in Indonesia/Mong	olia who have been primed through	previous vaccination with either of the included primary	
series. (Timepoint – 28 d	lays post vaccination)		
Estimand (for each trial vaccine):		The difference in seroresponse proportions 28 days after boosting with a single fractional dose compared to a single standard dose of either of the COVID-19 trial vaccines in adults 18 years or older in [Indonesia/Mongolia] who have been primed through previous vaccination with either of the included primary series, irrespective of SARS-CoV-2 infection.	
ESTIMAND Attributes:		Incorporation of Estimand Attribute in ANALYSIS:	
Treatment Fractional dose (for each	trial vaccine)	Study arms Interventions (for each trial vaccine): Fractional dose	
Target population		Comparisons (for each trial vaccine): Standard dose Analysis set ("Primary Day-28 Immunology	
	in Indonesia/Mongolia who have	Population")	
	evious vaccination with one of the	All randomised participants as per randomisation with	
included primary series.		complete outcome and covariate data	
Variable		Outcome measure	
Seroresponse in binding	antibodies 28 days after boosting.	Seroresponse in binding antibodies at the Day-28 visit	
		(28 – 35 days post-booster), defined as per Table 5.	
Handling of intercurrent	events	Handling of missing data	
Event (up to and	Strategy ^A	The proportion of participants excluded due to missing	
including Day-28 visit)		outcome or covariate data will be described by study	
		group.	
	Treatment Policy (interpret	If >5% of participants are excluded due to missing data,	
SARS-CoV-2 infection	results in conjunction with	a supplementary analysis will be performed with	
	breakthrough infection rates)	multiple imputation (Table 14).	
		marapie impatation (vasie 2 i).	
Population-level summa	ary measure	Analysis approach	
Difference in serorespon	se proportions	The difference between proportions will be estimated	
		with 95% confidence intervals using binomial	
		regression (identity link), adjusting for stratifying	
		variables (age group and primary series), duration	

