		between 1st and 2nd, and 2nd and 3rd doses, study day of	
		blood draw, and binding antibody level at baseline ⁶ : glm [seroresponse] [arm] [age group] [primary	
		series] [days 1st-2nd dose] [days 2nd-3rd dose]	
		[study day of blood draw] [baseline antibody], family(binomial) link(identity)	
		Results will be interpreted as described in Section 2.3	
		Framework.	

[&]quot;Supplementary analyses will be conducted using the Hypothetical Strategy for handling intercurrent events (see Table 14).

Table 11. Estimand-to-Analysis⁵ table for at least one solicited grade 3 or 4 local or systemic reaction within 7 days of boosting (primary reactogenicity endpoint)

Primary Objective (as per Protocol): Assess the rate and severity of reactogenicity within one-week post-booster f			
	daily, for seven days post vacci		
Estimand:		Incidence risk of a grade 3 or 4 local or systemic reaction within 7 days (inclusive) of boosting, by dosage (fractional or standard) and trial vaccine in adults 18 years or older in [Indonesia/Mongolia] who have been primed through previous vaccination with either of the included primary series.	
ESTIMAND Attributes:		Incorporation of Estimand Attribute in ANALYSIS:	
Treatment Fractional dose (for each	trial vaccine)	Study arms Interventions (for each trial vaccine): Fractional dose Comparisons (for each trial vaccine): Standard dose	
Target population Adults 18 years or older in Indonesia/Mongolia who have been primed through previous vaccination with one of the included primary series.		Analysis set ("Reactogenicity Population") All participants, as per trial vaccine received (regardless of allocation).	
Variable Grade 3 or 4 local or systemic reaction within 7 days (inclusive) of boosting.		Outcome measure Presence of at least one solicited grade 3 or 4 local or systemic reaction within 7 days (inclusive) of boosting.	
Handling of intercurrent	events	Handling of missing data	
Event (up to and including Day-7) SARS-CoV-2 infection Death	Strategy ^A While Negative (values up to the day of the first positive test are used) While Alive (values up to the time of death are used)	It will be assumed that participants with missing reactogenicity datapoints (collected daily for each reaction type) did not experience the specific reaction on the day/s where the value is missing. Missing data by day and reaction will be described by study group.	
Population-level summa	ry measure	Analysis approach	

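### The primary non-inferiority model (binomial, identity link, four continuous covariates) will usually fit probabilities above 1 or fail to converge at the planned 95% seroresponse; no fallback is given, and dropping the protocol's score-based interval is not listed as a change

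*SAP*

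**What the plan says.** SAP 6.13, Table 10, estimates the difference in Day-28 seroresponse by binomial "regression (identity link), adjusting for stratifying" variables and four continuous covariates: the interval between doses 1 and 2, the interval between doses 2 and 3, the day of blood draw, and baseline antibody. The code line ends "study day of blood draw] [baseline antibody], family(binomial) link(identity". No transformation of baseline is stated, although Table 12 logs it for the geometric-mean outcomes. The lower 95% limit is compared with -10% (SAP 2.3).

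Protocol 11.1 plans as follows: "Assuming a -10% non-inferiority margin and a seroresponse rate of 95% in both arms". It adds that "the study will have 90% power with 100 participants per group", and claims more than 99% with 200 per group. Protocol 11.3 leaves detailed methods to the SAP, but its rule for declaring non-inferiority says that "confidence intervals are calculated using Scorebased methods (12".

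SAP 6.1.1, "Summary of changes compared to the protocols", mentions neither the interval method nor the added adjustment. No section says what happens if the model fails or fits a value above 1; Table 14 deals only with intercurrent events and missing data. SAP 6.16 repeats the primary endpoint analysis within primary series (two strata have 100 per arm) and adds an interaction model.

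**The concern.** With 95% response there are only 5 points of room below the boundary, and an identity link lets a linear predictor cross it. When that happens the software may stop, hold the fit at the edge, or converge with a Wald interval that cannot be trusted. These outcomes can give different verdicts from the same data, and the SAP does not choose among them.

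A baseline effect is likely. Table 5 defines response relative to baseline and changes the threshold at 200 BAU/ml, so baseline is built into the outcome. Protocol 11.1 also expects a wide spread of pre-booster immunity in the Sinopharm-primed groups.

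This one interval carries the trial's main claim, so both false non-inferiority and lost power are at stake.

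**Working it through.** **1. The plan's own power figure.** Normal approximation, p = 0.95 in both arms, margin 0.10, one-sided 0.025:

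- 100 per arm: SE = √(2 × 0.95 × 0.05 / 100) = 0.0308; 0.10/0.0308 − 1.96 = 1.28; power 90.05%.
- 200 per arm: SE = 0.0218; 0.10/0.0218 − 1.96 = 2.63; power 99.6%.

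Both stated figures reproduce. Exact power with a score-based limit is lower: 83.2% at 100 per arm and 98.9% at 200. That gap is not due to the identity link and is the fair benchmark below.

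**2. Why fitted values cross 1.** As a rough guide, the average SE of a fitted value is √(p(1 − p)k/n), with k parameters and p = 0.95. Primary series counts as two indicators.

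- Full model, n = 800, k = 9: √(0.0475 × 9/800) = 0.023. The 0.05 of room is about 2.2 SEs.
- One stratum, n = 200, k = 7: √(0.0475 × 7/200) = 0.041. The room is about 1.2 SEs.
- Strata only, n = 800, k = 5: √(0.0475 × 5/800) = 0.017. The room is about 2.9 SEs.

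Participants with outlying covariates have larger SEs than average, so in the first two cases some will usually be fitted above 1.

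**3. How often it happens (simulation).** The documents give no covariate distributions, so these are assumed.

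- *Set A:* 1,000 trials per cell. Log-normal baseline with geometric mean 250 BAU/ml and SD(ln) 1.2; dose 1–2 interval 21 days plus gamma (mean 28); dose 2–3 interval 183 days plus gamma (mean 60); blood draw on days 28–35; strata as SAP Table 2; logit slope on ln baseline 0, -0.5 or -1; baseline entered raw or logged.
- *Set B:* 200–400 datasets per scenario, with different assumed intervals, SD(ln) 1, slope 0 or -0.7, and separate fitting code.

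Results at 95% response:

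- Set A, 400 per arm: fitted values outside 0–1 in 86–100% of trials. Iteratively reweighted fits did not converge in 30–64%.
- Set B: a fitted value of 1 or more in 84–100% at n = 800 and 99–100% at n = 200. The most favourable case (four bounded covariates, no effect) still gave 80% and 98%. Non-convergence or a missing SE occurred in 6–19%.
- Set B, strata-only identity model, n = 800: about 2–4%. The continuous covariates are the cause.

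**4. What it does to the verdict.** False non-inferiority at a true -10 points (target 2.5%), 400 per arm:

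| Method | Set A | Set B: no effect / baseline effect |
|---|---|---|
| Identity, unconstrained likelihood | 1.9–5.5% | not run |
| Identity, constrained to 0–1 | 4–51% | not run |
| Identity, reweighted with clipped fits | 9–44% (8–51% of converged) | 4.7% / 19.7% of converged |
| Logistic, standardised | 2.3–2.8% | 3.3% / 4.0% |
| Newcombe score interval | 2.1–2.5% | 3.5% / 2.5% |

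The 4% for the constrained fit is with no baseline effect. With a strong effect its mean estimate was -6.3 to -7.9 points instead of -10; logistic gave -10.1.

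At 100 per arm, Set B false non-inferiority (no effect / baseline effect) was 12.7% / 21.7% for the clipped identity fit, 4.5% / 2.2% for logistic and 2.8% / 1.0% for Newcombe.

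Power at 100 per arm with no true difference:

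| Method | Set A | Set B |
|---|---|---|
| Identity, unconstrained | 47–51% | not run |
| Identity, clipped, converged | not reported | 96–97% |
| Logistic, standardised | 88–92% (score fallback) | 89–90% |
| Newcombe score interval | 83–85% | 85–86% |

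Monte Carlo SE near 2.5% is about 0.5 points in Set A and, with 400 runs, √(0.025 × 0.975/400) = 0.8 points in Set B.

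**5. Lower response.** Set A at 85% in both arms with no baseline effect: out-of-range fits 13–36%, and identity-link verdicts matched logistic. With a strong baseline effect: still 90–100%.

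**The case against.** Several points on the other side have weight.

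- **Stata 17 was not run.** Its boundary handling is untested, and non-convergence differs widely between fitters (30–64% against 6–19%). Values above 1 are the usual outcome; outright failure is less certain.
- **The extremes depend on assumptions.** The 51% needs a strong baseline effect and a particular fitting rule. The unconstrained fit stayed at 1.9–5.5% although usually out of range, so a fitted value above 1 does not by itself make the verdict wrong.
- **The power loss comes from one rule and concerns the 100-per-arm strata.** Clipped fits gave 96–97% there. That is no reassurance, since the same fits falsely declared non-inferiority in 12.7–21.7%.
- **The simulated outcomes follow a logit model, which favours the logistic comparator.** The score interval assumes no such model and held at 1.0–3.5%. Generating response from the Table 5 thresholds instead also gave out-of-range or failed fits in 88–100% of datasets at n = 800.
- **The unlisted change carries a caveat.** The SAP cites version 4 of the Mongolia protocol, whereas the supplied protocol contains the 24-month extension. The version 4 wording on intervals cannot be checked.
- **Blinded safeguards exist.** SAP 3.5 says that "statisticians and analysts will develop and finalise all codes using a dummy variable for treatment allocation", and 6.1.4 has the primary analysis "independently double programmed by two analysts prior to unblinding using a randomly generated dummy variable for treatment allocation". Later revisions of comparative analyses go to staff without the real allocations. A failed fit would probably surface while analysts are blinded.

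The size therefore has to be read as a range. None of these points supplies a fallback, and two programmers running the same glm would agree on the same converged but wrong interval.

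**Conclusion.** The concern holds. At the sponsor's own planning rate, fitted probabilities above 1 or failed fits are the usual result, in roughly 84–100% of trials at 400 per arm and nearly always at 100 per arm. No rule says what to do then, and the move away from the protocol's score-based interval is not declared.

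Depending on the fitting rule and the strength of the baseline effect, false non-inferiority at the margin runs from near the 2.5% target to about half of trials. Under the unconstrained fit, power in the 100-per-arm strata is about half the planned 90%.

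These sizes rest on assumed covariate distributions, on fitters other than Stata, and on response near 95%. With response nearer 85% and no baseline effect the problem largely disappears. It should be settled before the model is run on real allocations, because this interval decides the primary claim.

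**What to change.** In Table 10, replace the glm line with logistic regression on the same covariates and state the form of baseline (for example ln). Obtain the marginal risk difference and 95% CI by standardisation; in Stata, logit with robust variance, then margins for the arm contrast with unconditional variance.

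Name the protocol's score-based interval as the sensitivity analysis. Name it also as the fallback for non-convergence or separation, including in the primary-series subgroups: logistic regression itself failed from separation in about 2% of the Set A trials at 100 per arm. List the change of method in 6.1.1.

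Making the score interval primary, with a stated convergence and range rule for any adjusted model, would also close the gap, at somewhat lower power (83–85% against 88–92% at 100 per arm).

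The cost is SAP wording and a few lines of code. No new data are needed, and the estimand and the -10% margin do not change.

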3.2 Outcomes

3.2.1 Primary outcomes

Immune response

Binding antibody – These will be evaluated using the commercial Euroimmun S1 IgG ELISA on all serum samples collected at 6 timepoints (baseline, 28 days, 6 months, 12 months, 18 months and 24 months). Assays for all subjects will be completed within 4 weeks of sample collection. Assays on the 28 days post-vaccination sample, comparing fractional and standard dose, will be reviewed by the DSMB.

Reactogenicity

Reactogenicity will be measured using the accepted standardised method to evaluate systemic and local side effects following vaccination using a structured questionnaire for days post-vaccination as outlined in Table 1 below.

Table 1. Grading system for evaluation of systemic and local side effects following vaccination (8).

Local Reaction to Injec	table Product ª			
				Potentially Life
	Mild	Moderate	Severe	Threatening
	(Grade 1)	(Grade 2)	(Grade 3)	(Grade 4)
Pain	Does not	Repeated use of	Any use of	ER visit or
	interfere with	nonnarcotic pain	narcotic pain	hospitalization
	activity	reliever >24	reliever or	
		hours or	prevents daily	
		interferes with	activity	
		activity		
Tenderness	Mild	Discomfort with	Significant	ER visit or
	discomfort to	movement	discomfort at rest	hospitalization
	touch			
Erythema/redness ^b	2.5 – 5 cm	5.1 – 10 cm	>10 cm	Necrosis or
				exfoliative
				dermatitis
Swelling ^c	2.5 – 5 cm	5.1 – 10 cm or	>10 cm or	Necrosis
	and does not	interferes with	prevents daily	
	interfere with	activity	activity	
	activity			
Hardness ^c	2.5 – 5 cm	5.1 – 10 cm or	>10 cm or	Necrosis
	and does not	interferes with	prevents daily	
	interfere with	activity	activity	
	activity			
Axillary	Does not	Repeated use of	Any use of	ER visit or
lymphadenopathy	interfere with	nonnarcotic pain	narcotic pain	hospitalization
	activity	reliever >24	reliever or	
		hours or	prevents daily	
		interferes with	activity	
		activity		
Warmth (usually	Absence		Presence	
reported with				
redness)				
Itch	Absence		Presence	

^a For all parameters, grade 0 will be recorded if specific symptoms are absent.

^b The measurement should be recorded as a continuous variable in addition to grading the measured local reaction at the greatest single diameter.

^c Hardness and swelling should be evaluated and graded using the functional scale as well as the actual measurement.

Systemic (General) ^a

				Potentially Life
	Mild	Moderate	Severe	Threatening
	(Grade 1)	(Grade 2)	(Grade 3)	(Grade 4)

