5.1.2 Reactogenicity within 7 days of boosting

Reactogenicity will be measured using a standardised daily questionnaire (diary card) that elicits the presence and severity (mild, moderate, severe, life-threatening [grades 1-4, respectively]), or absence, of local reactions (pain, tenderness, redness, hardness, swelling, necrosis, warmth, or itch at or near the injection site) or systemic reactions (fever, nausea, vomiting, diarrhoea, headache, fatigue/malaise, myalgia, arthralgia, or enlarged lymph nodes) within the last 24 hours on days 1 through 7. Warmth and itch will be recorded as presence/absence only (i.e., not graded). The primary endpoint for reactogenicity will be solicited grade 3 or 4 local or systemic reactions within 7 days of vaccination, inclusive.

Table 6. Primary endpoints

Primary Endpoint	Outcome	Timepoint	Population measure	Comparison	Measure of association
i.	Seroresponse (see Table 5)	Day-28 visit	% (95% CI)	Fractional vs. Standard	Difference in %
ii.	Reactogenicity: solicited grade 3 or 4 local or systemic reactions within 7 days of vaccination, inclusive	7 days post- booster	% (95% CI)	NA (descriptive)	NA (descriptive)

All analyses will be conducted separately for the different booster vaccines, amongst all strata combined, and then stratified by the primary series strata (see

Strategy for multiple imputation

Protocol Numbers:

81803 (V9), 81800 (V4), BCOV22 (V3)

Statistical Analysis Plan

Page 22 of 52

Multiple imputation will be done using a multivariate imputation model (MICE) and 50 imputations. Covariates in the imputation model will be the same as those specified for imputation under the hypothetical strategy (Section 6.15.1 Implementation of the Hypothetical Strategy). For the binary seroresponse outcome, binding antibody levels will be imputed (rather than the relative increase from baseline or binary seroresponse), and then seroresponse will be derived using the imputed value/s.

Subgroup analyses and tests for interaction).

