6.1.2 Framework

The primary endpoint is testing for non-inferiority in seroresponse, with a non-inferiority margin of -10%. The secondary endpoints are testing for superiority. The reactogenicity and safety endpoints are descriptive and will be interpreted in conjunction with the results of the primary and secondary endpoints.

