Incidence risk (proportion	n) of at least one solicited emic reaction within 7 days	Proportions will be estimated with 95% Clopper-Pearson binomial confidence intervals using the Ci Stata command.	
		Supplementary analysis: The following reaction-specific descriptive analyses will also be conducted: Number and percentage of individuals with each reaction type, presented in a radial graph (Dummy Figure 3). Number and percentage of participants with each reaction type, by severity grade (Dummy Figure S 3). Distribution of the day of onset for each reaction type Distribution of the duration of each reaction type	

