6.16 SUBGROUP ANALYSES AND TESTS FOR INTERACTION

Analyses will be conducted separately for each study (the Indonesia Trial, BCOV22 [concatenated with BCOV21], and the Mongolia Trial). Analyses will also be conducted on concatenated data of the Indonesia Trial and BCOV21/22.

Analyses for all endpoints will be conducted separately for the different booster vaccines, amongst all strata combined. Subgroup analyses by the primary series strata will also be conducted for the primary endpoints, and all binding antibody, ACE2 binding inhibition, safety and breakthrough infection secondary endpoints. Tests of interaction will be done for the primary immunogenicity endpoint and secondary endpoint (i) (see 5.2 Secondary) by fitting a model with an interaction parameter between study arm and primary series strata.

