6.18 ANALYSIS OF BREAKTHROUGH INFECTIONS

Table 15. Generic Estimand-to-Analysis table for all breakthrough infection endpoints for incidence risk (specified in Table 9).

(specified in Table 9).				
Primary Objective (as per Protocol): Identify any difference in the risk of clinically significant COVID-19 cases between any of the study groups [Indonesia Trial and BCOV22]; Evaluate the safety of the booster dose regimens [all studies]				
Estimand (for each trial vaccine):		Incidence risk of [OUTCOME]* to [TIMEPOINT]*, by dosage (fractional or standard) and trial vaccine in adults 18 years or older in Indonesia who have been primed through previous vaccination with one of the included primary series.		
ESTIMAND Attributes:		Incorporation of Estimand Attribute in ANALYSIS:		
Treatment Fractional dose (for each	trial vaccine)	Study arms Interventions (for each trial vaccine): Fractional dose Comparisons (for each trial vaccine): Standard dose		
Target population Adults 18 years or older in Indonesia/Mongolia who have been primed through previous vaccination with one of the included primary series.		Analysis set All randomised participants		
Variable		Outcome measure		
SARS-CoV-2 infection (bre		At least one positive SARS-CoV-2 test (PCR)		
Handling of intercurrent		Handling of missing data		
Receipt of 4 th dose (self-initiated)	Strategy ⁴ Treatment Policy (interpret results in conjunction with 4 th dose coverage)	Active surveillance for SARS-CoV-2 is not being done. Therefore, participants without a positive SARS-CoV-2 test will be included in the analysis under the assumption that they have not had a breakthrough infection.		
Receipt of 4 th dose (rescue) Treatment Policy (interpret results in conjunction with extent of rescue vaccination)				
Population-level summary measure		Analysis approach		
Incidence risk (proportion	n positive)	The incidence risk (a proportion) will be estimated in each group (arm [fractional or standard] and trial vaccine) with 95% CI using the proportion command in Stata. Analyses are descriptive only (no comparisons between arms will be made).		

^{*}This table is generic for all breakthrough infection endpoints for incidence risks (with varying combinations of outcomes & timepoints) specified in Table 9 as they will be analysed in the same way.

Table 16. Generic Estimand-to-Analysis table for all breakthrough infection endpoints for incidence rate (specified in Table 9).

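### SAP Table 11's denominator and missing-value rule count a participant with no diary data as a non-event for the primary grade 3–4 reactogenicity endpoint; the effect is downward and probably small

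*SAP*

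**What the plan says.** SAP 5.1.2 makes grade 3 or 4 solicited reactions in the first week one of the two primary endpoints. The data source is solicited and daily: "Reactogenicity will be measured using a standardised daily questionnaire (diary card) that elicits the presence and severity" of each reaction, or its absence. Table 1 in Protocol 3.2.1 adds that "For all parameters, grade 0 will be recorded if specific symptoms are absent", and Protocol 9.1.4 asks for missing data to be marked as missing on the eCRF. The database can therefore tell a blank from a recorded absence.

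SAP 6.13, Table 11, then sets out the analysis:

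- Analysis set: "All participants, as per trial vaccine received (regardless of allocation". No minimum of diary data is required.
- Missing data: the working assumption is "participants with missing reactogenicity datapoints (collected daily for each reaction type) did not experience the specific reaction on the day/s where the value is missing". Gaps are to be described by day, reaction and study group.
- Estimation: "Proportions will be estimated with 95% Clopper-Pearson binomial confidence intervals using the Ci Stata command".

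Table 11 names no sensitivity analysis for missing diaries. The >5% imputation analysis in SAP Table 14 has rows for immunological endpoints only. A footnote to the participant-flow list in SAP 6.6 speaks of noting the number with missing data and imputing in a sensitivity analysis above 5%. Its marker is not legible enough in the copy reviewed to show whether it attaches to the Reactogenicity and Safety Population.

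**The concern.** The missing-value rule is worded for single reactions on single days. With a denominator of everyone vaccinated, it also reaches the participant who supplies nothing: every reaction on every day is scored absent, so the week is scored as free of severe reactions. Missing data can remove events but never add them, so the error on a primary safety endpoint runs in one direction. What is at stake is the level of each arm's reported risk and the honesty of its interval, which counts unobserved people as observed. The same holds by priming vaccine, because "Subgroup analyses by the primary series strata will also be conducted for the primary endpoints".

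**Working it through.** **The plan's own figure.** Protocol 11.1 gives 95% half-widths of 6.9 points (n = 200) and 9.8 points (n = 100) at a reaction rate of 50%. The normal approximation, 1.96 × √(0.5 × 0.5 / n), gives 6.93 and 9.80, so the figures reproduce. The Clopper-Pearson interval used in Table 11 gives 7.13 and 10.17. These figures concern any reaction and take every participant as observed. They supply neither a grade 3–4 risk nor a missing-diary share, so both are assumed below.

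**Formula.** Let p be the true grade 3–4 risk and m the share of participants with no diary data, unrelated to outcome. A no-diary participant adds 0 to the numerator and 1 to the denominator, so Table 11 reports p(1 − m) on average. The analysis in those with diary data reports p.

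**400 per arm (SAP 3.3), Clopper-Pearson 95% intervals.**

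| p | m | Table 11 | Those with diary data |
|---|---|---|---|
| 10% | 5% | 38/400 = 9.5% (6.8–12.8) | 38/380 = 10.0% (7.2–13.5) |
| 10% | 10% | 36/400 = 9.0% (6.4–12.2) | 36/360 = 10.0% (7.1–13.6) |
| 5% | 10% | 18/400 = 4.5% (2.7–7.0) | 18/360 = 5.0% (3.0–7.8) |
| 20% | 10% | 72/400 = 18.0% (14.4–22.1) | 72/360 = 20.0% (16.0–24.5) |

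At p = 10% and m = 2% the expected figure is 0.10 × 0.98 = 9.8%.

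**Priming-vaccine subgroups, p = 10%, m = 10%.** With 200 per arm: 18/200 = 9.0% (5.4–13.9) against 18/180 = 10.0% (6.0–15.3). With 100 per arm: 9/100 = 9.0% (4.2–16.4) against 9/90 = 10.0% (4.7–18.1).

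**Coverage.** At 400 per arm and p = 10%, the nominal 95% interval under Table 11 covers the true risk 94.4% of the time at m = 5% and 90.7% at m = 10%. The diary-data interval covers about 96% in both cases.

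**Partly completed diaries.** If a share q of diary days is missing at random and the severe reaction lasts k days, the loss is p × q^k. At p = q = 10% this is 1.0 point for a one-day reaction and 0.1 point for a two-day reaction.

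**Return that depends on outcome, true risk 10%.**

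- Severe reactors return less (15% of them and 5% of the rest give no diary). Table 11: 0.10 × 0.85 = 8.5%. Diary data only: 0.085 / (0.085 + 0.90 × 0.95) = 0.085 / 0.940 = 9.0%. Both are too low.
- Non-returners had nothing to report (40 of 400, none with a severe reaction). Table 11: 40/400 = 10.0% (7.2–13.4), which is right. Diary data only: 40/360 = 11.1% (8.1–14.8), which is too high.

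**The case against.** The case for leaving Table 11 alone has weight. The rule is explicit and prespecified, and missingness will be described by arm. SAP 6.1.2 says that "The reactogenicity and safety endpoints are descriptive", so no test, margin or power figure depends on this proportion. Solicited events are documented at the vaccination visit and by phone on Day 1 and Day 7, with the diary read out or reviewed at the latter, and late information is taken at Day 28 (Protocol 7.1 and 7.2). No diary is therefore not the same as no information, and a 10% share wholly missing has no support in the documents. The SAP 6.6 footnote may already promise a count of missing data by group. Limiting the analysis to those with diary data is a post-randomisation exclusion, and as shown it can overstate the risk, which Table 11 cannot.

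Most of this stands as an argument about size and about showing both figures. It does not remove the miscount: describing missingness does not correct the headline percentage, and the footnote is not carried into Table 11 or Table 14. Nor does the precedent of SAP Tables 15 and 16 help. They also treat no record as no event, but the reason given there is that "Active surveillance for SARS-CoV-2 is not being done". A daily solicited diary with follow-up calls is a form of active collection.

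**Conclusion.** The point holds. Followed as written, Table 11 counts a participant with no diary data as a non-event and can only lower the reported grade 3–4 risk. Under the assumed 10% risk with diaries missing at random, the shift is 0.2, 0.5 and 1.0 point at 2%, 5% and 10% wholly missing, with an interval of roughly ±3 points at 400 per arm. The effect is probably at the low end of that range.

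Four stronger readings are tempting, and the documents do not support them:

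- *The exact interval is part of the cause.* It is not. The denominator and the missing-value rule suffice; the interval only inherits the full N.
- *The rule biases the comparison of doses.* Unequal missingness could create a gap (5% against 20% missing gives 9.5% against 8.0%). However, SAP Table 6 plans no comparison for this endpoint, and every blinding statement covers at least the diary week, so nothing suggests that return would differ by arm.
- *The analyst has conflicting instructions.* SAP 4.4 and 6.11 mention multiple imputation in general terms, but Table 11's own cell governs this endpoint. SAP 6.11 and Table 11 also class death differently. With deaths inside seven days expected to be very rare, that is a wording point only.
- *The diary-data figure is the correct one.* It is so only if diaries are missing at random.

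**What to change.** In Table 11, report the proportion and Clopper-Pearson interval in vaccinated participants with at least one completed diary day or a completed Day-7 review. Report the number with no diary data by arm. Show the all-participants result, with missing taken as absent, beside it, so that the reader sees how far the two differ. Single missing items or days within the diary-data set can keep the current rule; the residual loss is small unless severe reactions last only one day.

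The change needs SAP wording and minor programming on data already collected. The price is a slightly smaller denominator, slightly wider intervals (7.1–13.6 against 6.4–12.2 in the 400-per-arm example at 10% missing) and a missing-at-random assumption that should be stated. It does not cure return that depends on the outcome, which is why both figures should appear. If the Day-28 analysis has already been run, the added figure should be labelled as a later addition.
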